Baseline work-up (per NCCN guideline) within 28 days +/- 14 days prior to enrollment: CBC with Diff, CMP, Calcium, Albumin, Serum Protein analysis, Quantitative Immunoglobulin, Serum Immunofixation (SIFE), 24 hr urine total protein, Urine Immunofixation, Serum Free Light Chain, Bone Marrow Biopsy (with IHC, flow, cytogenetics, FISH),

Whole Body PET/CT, Biopsy of Osseous or extra-osseous site (only if clinically indicated);
Pregnancy test;

Inclusion Criteria:

- 1) ≥ 18 years old; ISS stage I-III multiple myeloma that has progressive, relapsed, or refractory disease;
- 2) Able to give informed consent;
- 3) ECOG 0-1;
- 4) Relapsed and/or refractory myeloma; There is no minimum or maximum number of previous therapies that a patient may have received previously before being put on the current trial.
- 5) ≥ 1 osseous and/or extra-osseous lesion that can be radiated;
- 6) Candidate for pembrolizumab (as determined by physician, and adequate organ function as noted in **Table 1**);
- 7) Candidate for radiotherapy (as determined by treatment physician); These patients can have symptomatic disease and/or asymptomatic disease. A minimum of one site of radiation is required to any osseous and/or any extra-osseous disease. Radiation to any bony parts of the Head and Neck, Skull, Spine, ribs, and/or extremities are allowed. Radiation to any bony part for documented lytic disease is allowed. Radiation to any soft tissue plasmacytoma (including osseous and extra-osseous plasmacytoma) is allowed. The only exclusion criteria for radiation, is CNS metastases (see exclusion criteria # 16);
- 8) Measurable myeloma disease (**urine protein > 200 mg in 24 hr urine collection, serum free light chain ratio > 100 with an abnormal k/l ratio, serum M protein > 0.5 g/dl**) ; **12 of the 24 patients do not have to have measurable disease;**
- 9) Negative urine pregnancy test within 2 weeks for female subjects;

Female subjects of childbearing potential should have a negative urine or serum pregnancy within 72 hours prior to receiving the first dose of study medication. If the urine test is positive or cannot be confirmed as negative, a serum pregnancy test will be required.

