3. OBJECTIVES, ENDPOINTS & HYPOTHESES

1. Primary Objective, Endpoint, & Hypothesis

Primary Objective

To evaluate the safety of concurrent single/low dose radiotherapy (**8 Gy/1fx**) in combination with Pembrolizumab in relapsed or refractory myeloma patients; **Once 10 patients are enrolled, we will stop trial for 3 months to assess for acute toxicity, and then resume the trial.**

Primary Endpoint

CTCAE > grade 2 toxicity at the specific irradiated **organ site at 3 months** (the Dose Limiting Toxicity);

Primary Hypothesis

The primary hypothesis of this pilot study is that the use of concomitant Pembrolizumab and radiation therapy in multiple myeloma patients will be well tolerated and safe.

Alternative Hypothesis

It is possible that concurrent use of radiotherapy and Pembrolizumab in relapsed/refractory myeloma may increase CTCAE > grade 2 toxicity within the radiated site at 3 months.

2. Secondary Objective(s), Endpoint(s) & Hypothesis (es)

Secondary Objectives

To characterize late toxicity (CTCAE > grade 2 toxicity at **6 and 12 months**) and the effect of radiation in combination with Pembrolizumab on systemic response rates using international myeloma working group (IMWG) uniform response criteria for multiple myeloma at **6 months and 12 months**;

To assess changes in PET/CT as a result of combining Pembrolizumab and radiotherapy at **6 months and 12 months**;

Secondary Endpoints

- a. 1. Number of patients achieving any response (from baseline) per IMWG response criteria at **6 months and 12 months**;
- b. 2. Overall survival time at **6 months and 12 months**;
- c. 3. Overall response based on baseline changes on PET/CT at **6 months and 12 months**;
- d. 4. Difference in pre and post treatment serum immune biomarkers;

Secondary Endpoint Definitions

- a. Response is defined per IMWG criteria, and will be calculated at **6 months and 12 months**;
- b. Overall survival will be defined as time from first treatment on cycle 1, day 1 to the earlier of date of death and/or last follow up at **6 months and 12 months**.
- c. Overall response will be defined using IMWG uniform response criteria.
- d. Several serum biomarkers will be analyzed.

Secondary Hypotheses

The secondary hypothesis is that low dose/single fraction (8Gy/1fx) will synergize with Pembrolizumab for a more effective anti-myeloma response per IMWG, via the radiation induced abscopal response.

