In the phase 1 study with 495 NSCLC patients¹², no grade 3 or higher CNS toxicities were noted. Furthermore, the toxicity profile was similar to that identified in the two melanoma studies. Most common grade ≥ 3 adverse events were fatigue (0.8%), decreased appetite (1.0%), nausea (0.8%), asthenia (1.0%), dyspnea (3.8%) and pneumonitis (1.8%). 1 patient who developed pneumonitis did die; overall, these findings demonstrate pembrolizumab is well tolerated and has similar toxicity profiles among the two histologies.

Keynote 023 (San Miguel et al. Blood 2015, 126:505), conducted an open phase 1, multi-center, non-randomized, dose escalation trial to evaluate the safety, toxicity, and tolerability of pembrolizumab in combination with lenalidomide and low-dose dexamethasone in patients with relapsed/refractory myeloma. A 2 mg/kg q 2 weeks as well as a fixed 200 mg dose of pembrolizumab doses were used in combination with lenalidomide and dexamethasone in myeloma patients. By July of 2015, 34 patients had been enrolled. No deaths of treatment discontinuation was noted. Most frequent AEs were: thrombocytopenia (47%), neutropenia (41%), fatigue (29%), anemia, hyperglycemia, and muscle spasms (23%). No dose limiting toxicity were noted in the 10 mg-lenalidomide cohort; The MTD/MAD was defined as 200 mg fixed dose; The objective response was 13/17 patients (76%) with 4 patients achieving a very good partial response and 9 patients achieving a partial response; The authors concluded that PD-1 blockade showed promising anti-myeloma activity in heavily pre-treated relapsed/refractory myeloma patients.

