The Exclusion Criteria describes other medications which are prohibited in this trial. There are no prohibited therapies during the Post-Treatment Follow-up Phase.

3. Administration of Pembrolizumab Beyond Progression

If the initial **week 6-week 8** myeloma labs show disease progression per IMWG response criteria, patients are allowed to continue treatment until progression is confirmed again at a **subsequent 4-8 week later**, to account for atypical response patterns (especially, if the clinician suspects, that there may still be a benefit to continue for a little bit longer). A physician would be allowed the choice to continue the patients on the current trial or removed from the trial;

If the repeat myeloma labs **beyond the 12 weeks** shows evidence of disease stabilization or objective response (relative to the previous scan that showed PD) as per IMWG response criteria, pembrolizumab may be continued per treatment calendar. However, if the repeat assessment at **12 weeks** per IMWG criteria shows disease progression relative to the previous labs that showed PD, then pembrolizumab should be discontinued;

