11. STATISTICAL ANALYSIS PLAN

1. Statistical Analysis Plan Summary

Study Design

The study is a pilot study to look at the safety of concurrent PD-1 inhibitor and SRS for relapsed/refractory myeloma. A total of 24 patients will be enrolled on the trial (20 is the minimum, with an additional 4 patients, to make for any attrition and/or loss to follow-up). 12 patients will be allowed to not have measurable myeloma disease in this trial. Once 10 patients are enrolled, we will stop trial for 3 months to assess for acute toxicity, and then resume the trial. The estimated exact Clopper-Pearson 95% confidence interval for a 20% rate based on 5 responses in 20 patients is (0.087, 0.491), with a precision of 0.185. If we see lower than 20% difference in rate of toxicity at 3 months, the combination will be deemed safe.

A minimum of 20 patients are required to complete full treatments. An additional 20% is allowed for drop out/failure to adhere to required follow-up and treatment recommendations. Thus, 24 patients will be allowed to be enrolled on the trial to make for any attrition and/or loss to follow-up. 12 patients will be allowed to not have measurable myeloma disease.

# of Responses / # of Patients	95% confidence interval
5 / 20	(0.087, 0.491)
6 / 24	(0.098, 0.467)

Populations for analysis

- Enrolled set: All subjects who signed an informed consent.
- Safety set: All subjects who received at least one dose of any study drug.
- Full analysis set: All subjects from the safety set who have the required follow-up and treatment adherence to evaluate response and safety over time.

2. Statistical Analyses

1. Response

IMWG criteria will be used to assess response. Proportion of patients achieving stable

disease or better will be reported at **6 months** and **12 months**; Response rates will be reported along with 95% confidence intervals will be estimated using the Clopper-Pearson method.

2. Safety

Proportion of acute (at **3 months**) and late toxicity (**6 and 12 months**) will be reported, and 95% confidence intervals will be estimated using the Clopper-Pearson method.

3. Overall Survival

For overall survival, death from any cause will be defined as the event. Patients will be censored at time of last follow-up. OS will be estimated using the Kaplan-Meier product-limit method. Overall survival will be analyzed at **6 months, and 12 months**.

4. Biological variables

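### The secondary response endpoint is stated inconsistently (threshold and response criteria), and no rule says how patients without measurable disease are scored

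*Combined protocol and SAP*

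**What the plan says.** **Threshold.** The first secondary endpoint in Section 3 is "Number of patients achieving any response (from baseline) per IMWG response criteria" at 6 and 12 months. The definitions below it leave response to IMWG and list no qualifying categories. Section 11, Statistical Analyses, item 1 (Response), opens "IMWG criteria will be used to assess response. Proportion of patients achieving stable" disease or better, at the same two times. After a semicolon it adds "Response rates will be reported along with 95% confidence intervals" by the Clopper-Pearson method.

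**Criteria.** Sections 3 and 11 name IMWG. Section 3 also lists an overall response based on PET/CT changes, yet its definition reads "Overall response will be defined using IMWG uniform response criteria". Appendix III says the investigator bases response on irRC and that irRC underlies the key efficacy endpoints. IMWG itself appears only as a web link in Appendix IV. The Trial Overview in Section 2 sends the reader to Appendix II for IMWG, but Appendix II is RECIST 1.1.

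**Denominator.** Inclusion criterion 8 states that "12 of the 24 patients do not have to have measurable disease", and Section 11 repeats the allowance. The Response item names no analysis set. The full analysis set is the only one whose definition mentions response: "All subjects from the safety set who have the required follow-up and treatment adherence to evaluate response and safety over time".

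**The concern.** Three things have to be fixed before a response rate means anything: which categories count, which criteria assign them, and who is in the denominator. Here the first two are given in ways that do not agree, and the third is not given for patients who may make up half the trial.

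The trial is open-label and single-arm, and the background section says the pilot is meant to inform later designs on early safety and efficacy. The secondary hypothesis in Section 3 is about a more effective IMWG response. If the same data can yield different response rates depending on which passage is followed, the choice could be made after results are known, and a later trial could be planned on a figure that includes stable disease without saying so.

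The full analysis set adds a further problem. It selects on what happens after treatment starts. Patients who stop early or miss follow-up leave the denominator, and if they are mostly non-responders the rate rises.

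**Working it through.** **1. The plan's own intervals.** The Clopper-Pearson 95% limits for x of n are the 2.5% quantile of Beta(x, n − x + 1) and the 97.5% quantile of Beta(x + 1, n − x). For 5/20 this gives 0.087 to 0.491 and for 6/24 it gives 0.098 to 0.467. Both match the table in Section 11.

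**2. Threshold passages side by side.** Section 3 counts any response; Section 11 reports stable disease or better.
- If the two clauses in Section 11 describe one output, stable disease counts as response there, against Section 3.
- If they describe two outputs, the second has no threshold in the documents.

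Elsewhere the protocol keeps the two ideas apart. The passage in Section 5 on treatment beyond progression speaks of labs whose result "shows evidence of disease stabilization or objective response", naming them as alternatives. Section 4.4 reports a myeloma study's objective response as 13 of 17, "with 4 patients achieving a very good partial response and 9 patients achieving a partial response": 4 + 9 = 13, and 13/17 = 76%, with no stable disease included. Neither passage defines this trial's endpoint, but both show the usage the authors adopt.

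**3. Effect of the threshold.** The documents give no expected response or stable-disease rate, so the counts are assumptions. Each patient with stable disease counted as a responder adds 1/24 = 4.2 percentage points. Take 3 responders and 6 patients with stable disease:
- any response: 3/24 = 12.5% (0.027 to 0.324)
- stable disease or better: 9/24 = 37.5% (0.188 to 0.594)

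**4. Effect of the denominator.** Take 3 responders, all with measurable disease:
- all 24 patients: 3/24 = 12.5% (0.027 to 0.324)
- full analysis set, if the 4 patients allowed for attrition are excluded and are non-responders: 3/20 = 15% (0.032 to 0.379)
- measurable patients only, if all 12 permitted places are used: 3/12 = 25% (0.055 to 0.572)

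With k of 24 patients lacking measurable disease, the ratio of the restricted to the unrestricted rate is 24/(24 − k). It runs from 1.0 at k = 0 to 2.0 at k = 12. The upper end is a cap set by the eligibility rule, not a forecast.

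**5. Precision if only measurable patients count.** The smallest planned number is the minimum of 20 patients less the 12 permitted places, 20 − 12 = 8; the largest is 24. At the 25% rate used in the plan's table:

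| x/n | 95% interval | half-width |
|---|---|---|
| 2/8 | 0.032 to 0.651 | 0.31 |
| 3/12 | 0.055 to 0.572 | 0.26 |
| 5/20 | 0.087 to 0.491 | 0.20 |
| 6/24 | 0.098 to 0.467 | 0.18 |

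Section 11 shows only the last two rows.

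**The case against.** The strongest reply on the threshold is that the semicolon in Section 11 separates two outputs, disease control and response rate, and that the response threshold is delegated to IMWG. That reading is possible. A reader might therefore infer either that the plan flatly defines stable disease as response, or that nothing is wrong. The documents establish neither. IMWG is only linked, so what it fixes cannot be checked here, and the trial's own text never names the categories that count.

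On irRC, the reply is that Appendix III is leftover text. It is not cited in the body, it refers to a Time and Events Schedule where this protocol has a Trial Flow Chart, that chart schedules an IMWG assessment and no irRC assessment, and the data-collection list captures no irRC measurements. This is probably right, and it would be too strong to say that the trial intends to analyse response by irRC. The appendix is nevertheless current and speaks of this study, so the conflict needs removing. The wrong appendix number in Section 2 is clerical.

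On the denominator, the reply is that the full analysis set is already defined for evaluating response. It is, but the Response item does not assign it, and it has no condition or scoring rule for measurable disease. It would also be wrong to conclude that the evaluable number will be 12, or that 12 is the floor: 12 is the cap on non-measurable patients, and at the 20-patient minimum as few as 8 could be measurable.

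Finally, response is secondary and descriptive with no test or decision rule. That stands and limits the consequence.

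**Conclusion.** The point holds as an inconsistency in the current text of a secondary endpoint. Section 3 and the Response item in Section 11 do not state the same threshold, Appendix III contradicts both on the criteria, and the scoring of up to 12 of 24 patients is unstated. The only set linked to response selects on post-baseline adherence.

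Under the assumed counts, the threshold could move the reported rate from 12.5% to 37.5%, and the denominator from 12.5% to 25%. These figures illustrate the size of the ambiguity and do not predict results. Whether the IMWG text settles the threshold or the scoring of non-measurable patients cannot be determined from the documents. Nothing in them shows that a favourable definition has been chosen or will be; the text only leaves room for it. The primary 3-month toxicity endpoint and the sample size are not affected. It should be fixed before analysis.

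**What to change.** 1. Make Sections 3 and 11 agree by listing the IMWG categories that count as response, for example partial response or better, which is how Section 4.4 counts it in the cited myeloma study. Report stable disease or better separately as disease control. State whether the PET/CT overall response is a separate measure.
2. In Appendix III, remove irRC as the efficacy basis or label it exploratory. Correct the Section 2 reference so that IMWG points to Appendix IV.
3. For response, use safety-set patients with measurable disease at baseline in place of the full analysis set, and count unassessed patients as non-responders. Report patients without measurable disease separately, and also show the rate over all safety-set patients. State whether the criterion 8 thresholds, now separated only by commas in Section 2 and Appendix VI, are joined by and or by or, since this denominator depends on it.
4. Give exact intervals over the possible evaluable numbers, 8 to 24, as tabulated above.

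The cost is wording in Sections 2, 3 and 11 and Appendices III and VI; no added patients or tests. The effects on the result run both ways: leaving stable disease out lowers the rate, restricting to measurable patients may raise it, and the interval widens when fewer patients are evaluable.

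Separately, the passages that apply IMWG, RECIST and irRC to progression, discontinuation and clinical care (Section 5 on treatment beyond progression, the withdrawal criteria in Section 7, and Appendix III) must be reconciled. No clinical rule is proposed here.

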12. LABELING, PACKAGING, STORAGE AND RETURN OF CLINICAL SUPPLIES

1. Investigational Product

The investigator shall take responsibility for and shall take all steps to maintain appropriate records and ensure appropriate supply, storage, handling, distribution and usage of investigational product in accordance with the protocol and any applicable laws and regulations.

Clinical Supplies will be provided by Merck as summarized in Table 7.

Table 7 Product Descriptions

Product Name & Potency	Dosage Form
Pembrolizumab 50 mg	Lyophilized Powder for Injection
Pembrolizumab 100 mg/ 4mL	Solution for Injection

2. Packaging and Labeling Information

Clinical supplies will be affixed with a clinical label in accordance with regulatory requirements.

3. Clinical Supplies Disclosure

This trial is open-label; therefore, the subject, the trial site personnel, the Sponsor and/or designee are not blinded to treatment. Drug identity (name, strength) is included in the label text; random code/disclosure envelopes or lists are not provided.

4. Storage and Handling Requirements

Clinical supplies must be stored in a secure, limited-access location under the storage conditions specified on the label.

Receipt and dispensing of trial medication must be recorded by an authorized person at the trial site.

Clinical supplies may not be used for any purpose other than that stated in the protocol.

5. Returns and Reconciliation

The investigator is responsible for keeping accurate records of the clinical supplies received from Merck or designee, the amount dispensed to and returned by the subjects and the amount remaining at the conclusion of the trial.

Upon completion or termination of the study, all unused and/or partially used investigational product will be destroyed at the site per institutional policy. It is the Investigator's responsibility to arrange for disposal of all empty containers, provided that procedures for proper disposal have been established according to applicable federal, state, local and

institutional guidelines and procedures, and provided that appropriate records of disposal are kept.

13.0 DATA AND SAFETY MONITORING PLAN

The Data and Safety Monitoring Committee (DSMC) of the Winship Cancer Institute will provide oversight for the conduct of this study. The DSMC functions independently within Winship Cancer Institute to conduct internal monitoring functions to ensure that research being conducted by Winship Cancer Institute Investigators produces high-quality scientific data in a manner consistent with good clinical practice (GCP) and appropriate regulations that govern clinical research. Depending on the risk level of the protocol, the DSMC review may occur every 6 months or annually. For studies deemed High Risk, initial study monitoring will occur within 6 months from the date of the first subject accrued, with 2 of the first 5 subjects being reviewed. For studies deemed Moderate Risk, initial study monitoring will occur within 1 year from the date of the first subject accrued, with 2 of the first 5 subjects being reviewed. Subsequent monitoring will occur in routine intervals per the [Winship Data and Safety Monitoring Plan \(DSMP\)](#).

The DSMC will review pertinent aspects of the study to assess subject safety, compliance with the protocol, data collection, and risk-benefit ratio. Specifically, the Winship Cancer Institute Internal Monitors assigned to the DSMC may verify informed consent, eligibility, data entry, accuracy and availability of source documents, AEs/SAEs, and essential regulatory documents. Following the monitoring review, monitors will provide a preliminary report of monitoring findings to the PI and other pertinent individuals involved in the conduct of the study. The PI is required to address and respond to all the deficiencies noted in the preliminary report. Prior to the completion of the final summary report, monitors will discuss the preliminary report responses with the PI and other team members (when appropriate). A final monitoring summary report will then be prepared by the monitor. Final DSMC review will include the final monitoring summary report with corresponding PI response, submitted CAPA (when applicable), PI Summary statement, and available aggregate toxicity and safety data.

The DSMC will render a recommendation and rating based on the overall trial conduct. The PI is responsible for ensuring that instances of egregious data insufficiencies are reported to the IRB. Continuing Review submissions will include the DSMC recommendation letter. Should any revisions be made to the protocol-specific monitoring plan after initial DSMC approval, the PI will be responsible for notifying the DSMC of such changes. The Committee reserves the right to conduct additional audits if necessary.

14.1. Data Collection:

Data that will be captured in OnCore for the following procedures

- Inclusion/Exclusion Criteria
- Vital Signs
- Weight
- Karnofsky Performance Status (KPS) & ECOG
- HBcAb, HepC Ab
- PET/CT Diagnostic Imaging [RECIST]
- Adverse Events Assessment
- CBC with differential

- CMP
- T3, FT4, TSH
- Pregnancy Test – urine or serum b-HCG
- Urinalysis
- Uric Acid, MG, Phos, Coags (PTT, PT, INR) - [seconds]
- Serum Biomarkers
- Osseous, extra-osseous, bone marrow biopsy (if done, and what date it was done)

